9.4 Study Size

Statistical power is driven by the number of confirmed cases and the ratio between the duration of the risk and control periods. In Table 3, we provide the estimated number of cases (i.e., vaccinated cases with an event in the risk or control interval) needed for a SCRI design to have 80% power under a range of assumed effect sizes and the proportion of the observation period in the risk interval (number of days in the risk interval/[number of days in the risk interval + number of days in the control interval]) [8].

Additionally, based on the range of assumed relative incidences, durations of the risk and control intervals, background rate, and assumed vaccine uptake, one could estimate the total population size of the catchment areas for the hospital sites needed to achieve the necessary sample sizes. Other approaches may be acceptable to estimate study size.

Table 3. Sample Size Needed to Achieve 80% Power for the Self-controlled Risk Interval Design

Proportion of the Observation Period in the Risk Interval	Relative Incidence	Sample Size (Number of Cases)
25%	1.5	230
25%	2	74
25%	2.5	41
25%	3	28
25%	3.5	21
33%	1.5	203
33%	2	68
33%	2.5	38
33%	3	27
33%	3.5	21
50%	1.5	194
50%	2	69
50%	2.5	41
50%	3	29
50%	3.5	23

[To be completed by the study investigator(s) based on assumptions regarding length of the risk and control intervals and effect estimate size at the time of the full protocol development.]

9.5 Data Collection and Management

Each site will transform their local patient level data into the VAC4EU common data model (CDM). A distributed common programme will be run locally at each site using data from the CDM, which will create the study variables from the CDM, create the analytic data set, and conduct the analysis. Aggregate results and summary estimates will be returned to a single coordinating centre for pooled meta-analysis and reporting.

Routine procedures will include checking electronic files, maintaining security and data confidentiality, following analysis plans, and performing quality control checks of all programmes. Each research partner will maintain any patient-identifying information securely on site according to internal standard operating procedures or guidance documents.

Security processes will be in place to ensure the safety of all systems and data. Every effort will be made to ensure that data are kept secure so that they cannot be accessed by anyone except select study staff.

Appropriate data storage and archiving procedures will be followed in each research centre, with periodic backup as appropriate. Standard procedures will be in place at each research centre to restore files in the event of a hardware or software failure.

[Investigators should modify this section as needed for the specific study; if specific procedures of the identified hospital sites are known, they can be included here]

9.6 Data Analysis

9.6.1 Descriptive Analysis

The number and proportion of cases in the study population will be output according to descriptive characteristics for each AESI under study. Temporal graphs will be output showing the number of cases by time of vaccination to time of event (in days) for each AESI under study.

9.6.2 Measures of Association

If the SCRI is used, conditional Poisson regression (conditioned on the individual) will be used to estimate incidence rate ratios and 95% confidence intervals for each outcome, with logarithm of time in each interval as the offset. If the CCO is used, conditional logistic regression (conditioned on the individual) will be used to estimate odds ratios and 95% confidence intervals for each outcome.

For the SCRI and CCO, time-varying confounders will be adjusted for in regression models. If applicable, in the SCRI, age and calendar time may be categorised into several categories, or treated as polynomial functions, with or without the use of splines in regression models. Both unadjusted and adjusted incidence rate ratios, by site and pooled across all sites, will be reported.

If the vaccinated case-coverage design is used, a logistic regression model will be fit for each AESI under study using separate summarised data sets. The data set for each AESI under study will have one record per risk set (i.e., case), with the outcome indicating whether vaccination occurred in the case's exposure or comparison window. The logarithm of the expected odds (i.e., logit) of vaccination inside the exposure window will be entered into the model as an offset term. For each case, this expected probability of vaccination inside the exposure window will be obtained from the reference population, as described in Annex 3. The model will include only an intercept with no covariate, with the following general form.

$$\text{Logit}(p_1) = \text{logit}(p_0) + \beta_0,$$

where p_1 is the observed probability of vaccination inside the exposure window among cases, p_0 is the expected probability of vaccination inside the exposure window among cases (based on vaccination data in the reference population), β_0 is the intercept; by exponentiating this coefficient, one obtains an odds ratio describing the association between vaccination and the outcome of interest occurring inside the risk interval.

Of note, the logistic regression model drops all cases for whom the expected probability of vaccination inside the exposure window is 0 or 1 (i.e., either everyone or no one is vaccinated inside the risk interval amongst the reference population), as these cases are noninformative.

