<Interim report 3>	
<Registration in the EU PAS Register>	
Final report of study results	

EMA = European Medicines Agency; EU PAS Register = European Union Electronic Register of Post-Authorisation Studies.

Note: Contracts between the sponsor and research organisation(s) and approvals by data protection, data custodian, ethics, and scientific review bodies are pending. Timelines may be impacted by approvals of these bodies, duration of contract reviews, and availability of data and staff at research institutions once contracts and approvals are finalised.

^a Start of data collection is “the date from which information on the first study subject is first recorded in the study data set or, in the case of secondary use of data, the date from which data extraction starts.” [1]

^b End of data collection is “the date from which the analytical data set is completely available.” [1]

7 Rationale and Background

The novel coronavirus SARS-CoV-2, the cause of COVID-19, has led to a global pandemic. Several COVID-19 vaccine candidates are currently under research and in development. COVID-19 vaccines may be licensed by the European Medicines Agency (EMA) after thorough review of data on quality, efficacy, and safety. Because the prelicensure period is short and the number of participants in clinical studies may be too small to enable the detection of extremely rare events, efficient monitoring of vaccine safety in the postmarketing phase will be needed, with the objective of identifying as rapidly as possible any unintended side effects of vaccination. Because it is likely that a large number of individuals would be vaccinated against COVID-19 as a preventive measure, it is crucial to detect even rare serious adverse events shortly after licensure.

As part of its preparedness activities, the vACcine Covid-19 monitoring readinESS (ACCESS) project has developed several template protocols that address vaccine coverage, vaccine effectiveness, and vaccine safety. To allow all countries to participate and to use maximum capacity in Europe, protocols are divided into those that use primary data collection (hospital based) and those that rely on the secondary use of population-based electronic health records databases.

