9.6.3 Data Integration

Results will be presented separately for each data source and pooled across data sources.

The method for pooling of results will depend on the data-sharing policies of each of the participating hospitals. If all sites are able to share individual-level data or aggregate data needed for the analysis (e.g., case counts by vaccination interval and covariate status), local investigators will transfer their site’s individual-level data to the study coordinating centre to contribute to an analysis with one-stage pooling.

If some or all sites do not allow the necessary patient-level or aggregate data to be shared, then data analysis could be performed by data custodians at their sites behind firewalls. Counts and coefficients would be shared with the study coordinating centre, and overall results would be summarised using meta-analytic techniques.

Alternatively, if some institutions are able to share the necessary patient-level or aggregate data and others are not, a hybrid approach for pooling of data could be taken [9]. Depending on data-sharing restrictions, local investigators would either transfer aggregated data to the study coordinating centre for further analysis and pooling, or they would run the same analyses locally and transfer coefficients and counts to the coordinating centre. Both the pooled odds ratios/incidence rate ratios and individual odds ratios/incidence rate ratios from sites would then be summarised in a meta-analytic technique.

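### Section 9.6 has no rule for a window without cases: hospitals with few cases then have no finite ratio, and pooling their coefficients pulls the result towards the null

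*Protocol*

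**What the plan says.** Section 9.6.2 fixes one regression per design. For the SCRI, "conditional Poisson regression (conditioned on the individual) will be used to estimate incidence rate ratios and 95% confidence intervals for each outcome". For the CCO, "conditional logistic regression (conditioned on the individual) will be used to estimate odds ratios and 95% confidence intervals for each outcome". For the vaccinated case-coverage design it fits a logistic model with the expected log-odds as offset: "The model will include only an intercept with no covariate, with the following general form". The type of confidence interval is not named for any design.

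The section handles one degenerate situation: "the logistic regression model drops all cases for whom the expected probability of vaccination inside the exposure window is 0 or 1". That concerns the reference population. It does not cover observed cases that all fall on one side.

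On reporting, section 9.6.2 states: "Both unadjusted and adjusted incidence rate ratios, by site and pooled across all sites, will be reported". Section 9.5 describes a common programme run at each site, with summary estimates returned for a pooled meta-analysis. Section 9.6.3 allows one-stage pooling if all sites can share the data. If they cannot: "Counts and coefficients would be shared with the study coordinating centre, and overall results would be summarised using meta-analytic techniques". A hybrid of the two routes is also allowed.

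Section 7 states the aim: "it is crucial to detect even rare serious adverse events shortly after licensure".

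**The concern.** A rare event studied hospital by hospital gives small counts. When the control or comparison window is empty, the likelihood keeps rising as the ratio grows, so software stops at an arbitrary large coefficient with a very large standard error. When the risk window is empty, the same happens towards zero.

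A single such site is a nuisance. The larger risk is in pooling. A site with a huge standard error has almost no inverse-variance weight, whether or not anyone drops it on purpose. If vaccination does raise the risk, the sites lost this way are mostly those where every case fell in the risk window, so the loss has a direction: the pooled ratio moves towards 1.

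**Working it through.** **Inputs.** Table 3 (section 9.4) gives risk shares r of 25%, 33% and 50%, relative incidences (RI) of 1.5 to 3.5, 80% power, and 21 to 230 cases. Alpha is not stated; two-sided 0.05 is assumed, to match the 95% intervals. Site sizes are not given; 3 and 5 cases per site and 10 sites are assumptions. Section 9.6.3 does not name the meta-analytic method; inverse-variance weighting of log-ratios is assumed.

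**1. Table 3 reproduced.** The signed-root-likelihood formula is n = (1.960 + 0.842·√B)²/A, with p = RI·r/(RI·r + 1 − r), A = 2[p·ln RI − ln(RI·r + 1 − r)] and B = (ln RI)²/A × RI·r(1 − r)/(RI·r + 1 − r)². For r = 50% and RI = 3.5: p = 0.778, A = 0.327, B = 0.830, n = 22.74, rounded up to 23 as printed. All 15 cells match (with r = 0.33 in the middle block).

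**2. No finite estimate.** With n of n cases in the risk window the conditional log-likelihood is n·ln p, which rises without a maximum as the ratio grows. Test fits for 8 of 8 with equal windows stopped at a log-ratio of 11.2 (SE 97) for the SCRI and CCO models, and 22.6 (SE 17,040) for the case-coverage model. With 7 of 8 all three gave 1.946 (ratio 7.0, SE 1.07).

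**3. What remains finite.** For n of n, the exact lower limit is pL/(1 − pL) × (1 − r)/r with pL = 0.025^(1/n). The profile limit uses pL = exp(−3.841/(2n)). With equal windows:

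| Cases | Exact lower limit | Profile lower limit | Highest Wald lower limit from a table with a finite ratio |
|---|---|---|---|
| 6 | 1.18 | 2.65 | 0.58 |
| 7 | 1.44 | 3.17 | 0.72 |
| 8 | 1.71 | 3.69 | 0.86 |

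With the 42- and 85-day windows of section 9.2.5.3 and 5 of 5 cases in the risk window, the exact limit is 0.916 × 85/42 = 1.85 and the profile limit is 4.32.

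**4. How often.** P(all n in the risk window) = pⁿ.
- At Table 3 sizes the largest value is (3.5/4.5)^23 = 0.31%. Every other cell is below 0.03%.
- At RI 3.5 and 5 cases: 4.5% (r = 25%), 10.4% (33%), 28.5% (50%).
- At RI 3.5 and 3 cases: 15.6%, 25.8%, 47.1%.
- Empty risk window, with no effect and r = 25%: 0.75³ = 42% of sites with 3 cases.

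**5. Effect on pooling.** Take equal windows, RI 3.5 and 5 cases per site. The probabilities of 5, 4, 3, 2 and 1 cases in the risk window are 0.2846, 0.4066, 0.2323, 0.0664 and 0.0095. A site with x of 5 has weight x(5 − x)/5. The 5-of-5 sites have weight zero.
- Mean weighted log-ratio: 0.4066·0.8·ln 4 + 0.2323·1.2·ln 1.5 − 0.0664·1.2·ln 1.5 − 0.0095·0.8·ln 4 = 0.521.
- Mean weight: 0.8·(0.4066 + 0.0095) + 1.2·(0.2323 + 0.0664) = 0.691.
- With many sites the pooled ratio therefore tends to exp(0.521/0.691) = exp(0.754) = 2.1, although the true value is 3.5.

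Simulated medians for 10 sites agree:

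| RI | Cases per site | Sites with all cases in the risk window | Inverse-variance median | One-stage median |
|---|---|---|---|---|
| 3.5 | 5 | 28.5% | 2.2 | 3.5 |
| 3.5 | 3 | 47.1% | 1.5 | 3.3 |

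The first row has 50 cases in total, more than twice the 23 that Table 3 requires. Penalised (Firth) site coefficients, which keep every site, still pool to only 2.4 in that row. Part of the pull comes from small-count weighting itself, so rescuing the separated sites' coefficients is not enough.

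**The case against.** A reader might infer that the planned analysis returns no result exactly when the signal is strongest, or that it has no power in small samples. The documents do not support that. Section 9.6.2 does not prescribe Wald intervals, and a profile-likelihood lower limit from the same models is finite (3.69 for 8 of 8, with a likelihood-ratio statistic of 11.1). The graphs of days from vaccination to event (section 9.6.1) and the counts sent to the coordinating centre would still show the pattern. In a one-stage analysis a single control-window case at any site restores a finite unadjusted ratio.

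Comparisons at a relative incidence of 10 with 6 to 10 cases would also mislead, because they lie outside Table 3. At 3.5 with equal windows, the chance that 6, 7 or 8 cases all fall in the risk window, the only result there that an exact interval can separate from 1, is 22%, 17% and 13%.

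The other serious objection is that interval type and sparse-data rules are usually left to the SAP, and that this is a template to be completed. That stands for the interval type alone. It does not remove the point. The protocol itself fixes the estimators, requires ratios by site, describes pooling of site estimates, and writes a rule for one degenerate case but not for this one. It also does not fix inverse-variance weighting, so a likelihood-based meta-analysis would already comply. The bias in step 5 is what follows from the usual reading, not from an explicit instruction.

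**Conclusion.** The models suit the designs, and a one-stage analysis at the planned sizes is safe. The weakness is at site level: no rule covers an empty window, and under the distributed route the usual pooling of coefficients is biased towards the null when hospitals contribute few cases. At a relative incidence of 3.5 with equal windows and 10 sites of 5 cases, the median is about 2.2 instead of 3.5. With 3 cases per site it is 1.5 instead of 3.3.

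The frequencies in step 4 follow from the binomial model and the assumed site sizes. The pooling figures rest also on the assumed number of sites, on inverse-variance weights and on a ratio common to all sites. Fewer, larger hospitals would shrink the problem, and so would a smaller risk share: with 5 cases, 4.5% of sites have all cases in the risk window at r = 25%, against 28.5% at 50%.

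**What to change.** **Section 9.6.2.** State that when either window has no cases, the unadjusted result is reported with an exact conditional or profile-likelihood 95% interval, one limit being infinite or zero. Name which of the two is used. In the case-coverage design the exact version uses the Poisson-binomial distribution with each case's own expected probability, since a single binomial does not apply. Adjusted models use penalised likelihood with profile intervals.

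**Section 9.6.3.** State that the unadjusted pooled ratio is estimated from the site counts in a one-stage conditional likelihood, and not by inverse-variance pooling of coefficients. Counts are already among the items shared; specify that they are cases per window. For the case-coverage design, sites would send the expected probabilities or their log-likelihood over a grid of ratios.

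The rule should apply to an empty window only. A wider trigger, such as exact limits whenever a window has fewer than 5 cases, costs power: with equal windows, 14 cases and a relative incidence of 3.5, the chance of a lower limit above 1 falls from 59% (Wald) to 37% (exact). The Wald upper-tail error there is 2.9%, only slightly above the nominal 2.5%.

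The cost is a little extra code and, where exact limits are chosen, some conservatism.

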9.2.5.4 Vaccinated Case-Coverage Design

For the vaccinated case-coverage analysis, exposure and comparison windows will be defined using the same guidance and considerations as the CCO design, and cases that were vaccinated in either window will be informative to analysis. For each case, the observed odds of vaccination within the exposure window will be estimated and compared with an expected odds of vaccination inside the exposure window, which will be estimated in an external reference population. Data to estimate the expected odds of vaccination may come from population-based registers or surveys, or other secondary data sources that reflect temporal patterns in vaccination among the target population in the catchment areas for cases.

To calculate the expected odds of vaccination in the exposure window for each case, strata comprising all persons in the reference population who are similar to the case with respect to confounder status (e.g., age, sex, and risk factors) on the day of outcome onset will be created. Then the odds of vaccination in the same calendar period equating to the case's exposure window will be computed in the reference population. Reference population individuals in the stratum had to have received the same vaccine during the same calendar periods equating to the exposure or comparison windows before the onset of the case onset date and had to belong to the same groups as the case with regard to predefined confounding factors (e.g., age, sex, high-risk conditions). These predefined confounding factors will be selected on the basis that temporal patterns in vaccination are likely to be different across different levels of the confounder. Of note, this design requires information on vaccination in the reference population by risk factors and calendar date of vaccination. It is anticipated that these data will not be available for the catchment areas of most hospital sites.

Further Considerations for all Designs

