The vaccinated case-coverage design is predicated on the assumption that vaccination trends over time in the reference population reflect that of the cases. Bias due to the absence of this assumption should be minimised by matching cases to the reference population on important characteristics that are associated with the outcome and that may affect timing of vaccination (e.g., age or chronic conditions).

An anticipated challenge of the vaccinated case-coverage design in hospital-based studies is that it is likely to be difficult to identify appropriate data sources to estimate temporal trends in vaccination among groups of vaccinees defined by key confounders in catchment areas for participating hospitals; data on the number of vaccinations by calendar day and important risk factors are needed to implement this approach. Such data may come from population-based immunisation registers or other secondary data sources that capture vaccine coverage over time in samples representative of the target population.

Other Study Designs Considered but Excluded From This Template

The traditional SCCS was considered for inclusion in this template, but it has been excluded because it would require longitudinal data on vaccinations both before and after adverse events occur (i.e., both before and after hospital discharge) during the full study period. It is anticipated that this will not be possible without the use of immunisation registers, which are not available in many settings. Additionally, the SCCS provides less timely results than the SCRI because it requires a longer observation period in cases to accrue than the SCRI.

**Annex 4. Preliminary Assessment of Suitability of the
SCRI, CCO, and Vaccinated Case-Coverage
Designs to Study AESIs**

Table 4-1. Preliminary Assessment of the Suitability of the SCRI, CCO, and Vaccinated Case-Coverage Designs, by Study Outcome

Outcome	Suitability of SCRI (With Postvaccination Control Window)	Suitability of the CCO/Vaccinated Case-Coverage Design	Notes
Enhanced disease following immunisation	X	X	Requires unvaccinated comparator to identify whether disease is “enhanced” following vaccination
Multisystem inflammatory syndrome in children	✓	✓	
Acute respiratory distress syndrome	✓	✓	
Acute cardiovascular injury, including microangiopathy, heart failure, stress cardiomyopathy, coronary artery disease, arrhythmia	✓	✓	

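### The vaccinated case-coverage model treats an estimated reference odds as known, so its model-based interval is too narrow when reference vaccinees are few relative to the cases that share them

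*Protocol*

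**What the plan says.** Section 9.6.2 fits one logistic model per adverse event, with one record per case. The response is whether vaccination fell in the exposure or the comparison window. "The model will include only an intercept with no covariate". On the reference odds it says: "The logarithm of the expected odds (i.e., logit) of vaccination inside the exposure window will be entered into the model as an offset term". The form is logit(p1) = logit(p0) + β0. The section adds that "the logistic regression model drops all cases for whom the expected probability of vaccination inside the exposure window is 0 or 1" and calls those cases noninformative.

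Section 9.2.5.4 describes the expected odds as a quantity "which will be estimated in an external reference population". On the source it says: "Data to estimate the expected odds of vaccination may come from population-based registers or surveys, or other secondary data sources". Annex 3, on the same design, also accepts sources that "capture vaccine coverage over time in samples representative of the target population". The stratum behind each p0 is narrow: "Reference population individuals in the stratum had to have received the same vaccine during the same calendar periods equating to the exposure or comparison windows", and they must match the case on confounders such as age, sex and high-risk conditions. Section 9.6.4 redefines the strata again for subgroups.

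Sections 9.6.2 to 9.6.5, section 9.8 and Annex 3 do not mention the sampling error of p0, a minimum stratum size or a survey-design variance. The limitations in 9.8 cover representativeness, data availability and power.

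**The concern.** An offset has its coefficient fixed at 1 and is treated as known exactly. If p0 is the share vaccinated in the exposure window among m sampled vaccinees, it has its own binomial error. Every case that uses the same reference people inherits the same error, so adding cases to a stratum does not average it out.

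Table 2 makes this design primary whenever temporal trends are observed and stratified vaccination data exist, and Annex 3 calls changing vaccination likelihood highly plausible. Intervals that are too narrow give false safety signals too often. They also misweight sites in the meta-analysis of section 9.6.3, where sites that cannot share data send counts and coefficients and reference counts are not named. The drop rule carries a second risk, in the opposite direction: it can mask a real association.

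**Working it through.** **The plan's own figure.** Table 3, for the self-controlled risk interval (SCRI) design, is the only computed table. Take p = RI·r/(RI·r + 1 − r), A = 2[p·ln RI − ln(RI·r + 1 − r)], B = (ln RI)²·p(1 − p)/A and n = (1.96 + 0.8416·√B)²/A, with two-sided alpha 0.05 assumed. For r = 25% and RI = 1.5, n = 229.4, which rounds up to the stated 230. All 15 entries reproduce. Table 3 is not at issue; it only sets the scale of case numbers (21 to 230).

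**Inputs.** The model form is from 9.6.2 and the source of p0 from 9.2.5.4 and Annex 3. Case numbers of 70 and 200 are illustrative, within the range of Table 3. The reference size m is an assumption.

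**Fully shared strata, closed form.** For n cases sharing one stratum of m reference vaccinees:
- variance reported by the offset model: 1/[n·p1(1 − p1)]
- actual variance: that plus 1/[m·p0(1 − p0)]

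With an odds ratio of 1, p1 = p0 and the ratio of true to reported standard error is √(1 + n/m). With S equal strata of similar p0 it is √(1 + n/(S·m)). Coverage is 2Φ(1.96/ratio) − 1.

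One stratum, n = 70:

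| m | SE ratio | Coverage |
|---|---|---|
| 50 | √2.4 = 1.55 | 79% |
| 200 | √1.35 = 1.16 | 91% |
| 1,000 | √1.07 = 1.03 | 94% |
| 10,000 | √1.007 = 1.003 | 95% |

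Simulation with 4,000 replicates and p0 of 0.25-0.50 gives 64%, 80%, 86%, 94% and 95% at m = 20, 50, 100, 500 and 5,000.

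Several strata (simulation with p0 of 0.2-0.6):

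| Cases, strata | m per stratum | SE ratio | Coverage, formula | Coverage, simulated |
|---|---|---|---|---|
| 70, 5 | 20 | √1.7 = 1.30 | 87% | 85% |
| 70, 5 | 50 | √1.28 = 1.13 | 92% | 91% |
| 200, 10 | 20 | √2 = 1.41 | 83% | 82% |
| 200, 10 | 50 | √1.4 = 1.18 | 90% | 89-90% |
| 200, 10 | 100 | √1.2 = 1.10 | 93% | 92-93% |

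**Windows that follow each onset.** The protocol anchors the calendar windows to each case's onset, so cases in one confounder group share reference people only where their windows overlap. The simulation reused one reference sample per group, with 42-day windows, a 180-day period, rising uptake, uniformly spread onsets, an odds ratio of 1 and 1,000 replicates:
- 70 cases, 5 groups: 94% at mean m of about 19 and of about 47
- 200 cases, 10 groups: 92%, 93% and 95% at mean m of about 19, 47 and 93

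With clustered onsets and the same case and group numbers, coverage was about 91-95%. With many clustered cases in few groups it was about 65-92%. As onsets bunch more tightly, results move towards the fully shared figures. At the other extreme, with an independent stratum for each of 70 cases, coverage was 92% at m = 10, 94% at m = 20 and about 95% from m = 50.

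**Survey design effect.** With four shared strata, 70 cases and a design effect of 2, coverage falls from 91% to 87% at m = 50 and from 94% to 91% at m = 100.

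**Sampled zeros.** Assume true p0 uniform on 0.03-0.15, m = 20, 200 cases in 10 strata and a true odds ratio of 2. The chance that a stratum shows no vaccinee in the exposure window is (0.97²¹ − 0.85²¹)/(21 × 0.12) = (0.528 − 0.033)/2.52 = 0.20, so about 20% of cases are dropped. The strata kept are those where p0 happened not to be estimated as zero, so their offsets run high. The mean log odds ratio was 0.53 against a true 0.69, an odds ratio of about 1.7 instead of 2, with coverage of 77%.

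**The case against.** The strongest reply has four parts.

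- **No stated interval.** Section 9.6.2 promises 95% confidence intervals only for the SCRI and case-crossover designs. A reader might infer that the protocol states a wrong interval for the vaccinated case-coverage design. It does not, and a statistical analysis plan could supply a method. This stands, so the point concerns the interval that follows from the model as written. That model is fixed in the protocol.
- **Calendar matching.** A reader might take 82-85% coverage as typical of small reference samples. Those figures need fully shared strata. With windows moving with onset and cases spread over several groups, most of the loss disappears. This also stands, except for clustered onsets in few groups.
- **Small m is assumed.** Section 9.1 requires stratified vaccination data from the catchment population, and Table 2 otherwise sends the analysis to the SCRI. That makes very small references less likely. But no minimum size is set, and surveys and samples are expressly allowed.
- **Dropped cases are disclosed.** Section 9.8 notes that such cases are uninformative and cost power. It does not separate a true 0 or 1 from a sampled one, and it does not mention bias.

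**Conclusion.** The concern holds in a limited form. The direction is certain: the omitted variance term is positive whenever p0 comes from a finite sample. Its importance depends on m relative to the number of cases that share the same reference people.

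- Complete register, or about 1,000 or more vaccinees per stratum: negligible at the case numbers considered.
- m of 20 to 100, own-onset windows, several groups: modest, about 91-95%.
- Many clustered cases in few groups: about 65-92%.
- Strata fully shared, 5 to 10 of them: about 82-92%.

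These ranges rest on assumed values of m, p0, uptake and onset pattern, none of which the protocol gives. The documents do not support the reading that every use of a survey produces materially false signals. The bias from dropping sampled zeros is shown in one unfavourable setting with low p0; it is a possibility, not a forecast. The point should be settled before a study adopts the template, but it does not undermine the design.

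**What to change.** In section 9.6.2, state that when p0 does not come from a complete register, the interval will come from one of:
- a bootstrap that resamples cases and reference individuals together, respects the survey design, and reuses the same reference resample for all cases with overlapping windows; or
- a joint likelihood that uses the reference counts.

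A delta-method term, the sum over strata of (share of information)²/[m·p0(1 − p0)], should be used only where strata do not overlap and there is no survey design effect, because it assumes independent binomial strata.

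In section 9.6.3, have sites return the reference counts per stratum, so that the coordinating centre can compute or check the variance.

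Replace the drop rule: exclude a case for p0 of 0 or 1 only when the value is structural, for example because the product was not available in that window. Otherwise use a prespecified method, such as a continuity correction or coarser confounder strata within the same calendar windows, and report how many cases are affected.

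The cost is wider intervals, a little more code and, if strata are coarsened, somewhat looser confounder matching.
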